APPENDIX 2 MISSING AND PARTIAL RADIOTHERAPY AND SURGERY DATES IMPUTATION ALGORITHMS

Procedures – Imputation Rules.

If reported procedure start date is a full valid date then set start date equal to the date part of procedure start date.

In case of partial date use imputation rules described below:

- If only day is missing then
 - If month and year of procedure match month and year of first dose date then impute as date of first dose;
 - If month and year of procedure don't match month and year of first dose date then impute as first day of that month and year.
- If both day and month are missing, then impute as maximum between 01JAN of the year and date of the first dose;
- If date is completely missing or invalid then leave missing.

Note: Imputation is not applicable to data where start date is not collected (for example "PRIOR RADIOTHERAPY" CRF). Set start date to missing in this case.

If reported end date is a full valid date then set end date equal to the date part of the reported end date.

In case of partial date use imputation rules described below:

- If reported end date is partial then set end date equal to the last possible reported end date based on the partial entered reported end date.
- If reported end date is missing, continuing, unknown or invalid then set end date equal to the most recent database extraction date.

If end date was imputed then compare end date to the death date or last known alive date if subject is not dead. If posterior then end date should be imputed to death date (or last known alive date if subject not dead).

Note: Imputation of partial dates only applies to data entered on "RADIOTHERAPY" CRF page. For other CRF pages in case of partial dates set end date to missing.

Surgeries – Imputation Rules.

If reported surgery date is a full valid date then set start date equal to the date part of surgery date.

In case of partial date, use one of the two imputation rules described below:

A. For data collected on "PRIOR SURGERY RELATED TO CANCER" CRF page:

- If only day is missing then impute as the first day of the month;
- If both day and month are missing then then impute as 01JAN of the year;
- If date is completely missing or invalid then leave missing.

B. For data collected on other CRF pages (deemed to be on-treatment/subsequent surgeries):

- If only day is missing then
 - If month and year of surgery match month and year of first dose date then impute the missing date as the date of first dose;
 - If month and year of surgery don't match month and year of first dose date then impute as first day of that month and year;
- If both day and month are missing then impute as maximum between 01JAN of the year and date of the first dose;
- If date is completely missing or invalid then leave missing.

[REDACTED]

[REDACTED]

[REDACTED]

[REDACTED]

[REDACTED]

[REDACTED]

[REDACTED]

[REDACTED]

[REDACTED]

[REDACTED]

[REDACTED]

[REDACTED]

[REDACTED]

[REDACTED]

[REDACTED]

[REDACTED]

[REDACTED]

[REDACTED]

[REDACTED]

[REDACTED]

[REDACTED]

[REDACTED]

- [REDACTED]
- [REDACTED]
- [REDACTED]

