		
• Updated the abbreviations list• Revised the Appendix 2 (Safety Management Algorithms)• Added Appendix 3 (Women of Childbearing Potential and Methods of Contraception)• Other minor changes incorporated into this amendment include changes in document names, study materials that will be provided to sites, removal of duplicate statements, revisions to section numbering, and formatting changes
Administrative Letter 01	10-Feb-2016	
• Fixed the protocol title• Removed the reference to neck as an anatomical imaging area for the CT/MRI scan• Updated a section number
Original Protocol	06-Jan-2016	Not applicable

OVERALL RATIONALE FOR REVISED PROTOCOL 04

The rationale for the change to the overall survival (OS) final analysis (FA) trigger includes factors observed during the conduct of the trial. The actual OS event accrual in the study has been much slower than projected. Initial projections for the OS FA estimated [REDACTED]

Blinded

OS event tracking commenced in 2021 after the first planned interim analysis was completed. While Bristol-Myers Squibb (BMS) remains blinded to the number of OS events by treatment arm, the overall accrual of events has slowed significantly year over year, since tracking began. [REDACTED]

The treatment landscape has changed markedly since the study was designed. Patients who experience recurrence after adjuvant therapy have increased treatment options and can receive subsequent therapy with immune checkpoint inhibitors (ICI) or a combination of immune checkpoint inhibitors with chemotherapy. A portion of patients may also be cured with treatment. Increased treatment options may reduce disease mortality, therefore impacting the OS event rate.

Protocol Amendment 04 adds the option to conduct a time-driven analysis. [REDACTED]

SUMMARY OF KEY CHANGES FOR REVISED PROTOCOL 04		
Section Number & Title	Description of Change	Brief Rationale
Title Page	Updated European Union (EU) Trial Number. Updated Medical Monitor address.	Administrative update.
Synopsis Statistical Considerations	Added the option to conduct overall survival (OS) final analysis (FA) [REDACTED]	Refer to the overall rationale for revised protocol.
Section 2.1: Good Clinical Practice Section 6.1.1: Serious Adverse Event Collection and Reporting	Replaced Directive 2001/20/EC with European Regulation 536/2014.	To update the legal framework of the trial after transition to EU-CTR.

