5.4.1 Definitions of Recurrence

Recurrence is defined as the appearance of one or more new lesions, which can be local, regional, or distant in location from the primary resected site (confirmed by imaging or cytology/pathology).

Local or regional recurrence: Any anastomotic recurrence or/and occurring either in the mediastinum or upper abdomen at the site of previous esophageal resection and nodal clearance or in the cervical area where no lymphadenectomy had been performed.

Distant metastasis: Any recurrence occurring in distant organs, pleura and peritoneum. If both loco-regional recurrence and distant metastases occurred, the case was considered as distant metastases.

Diagnosis of recurrence should be unequivocal. If a new lesion is equivocal, for example because of its small size or ambiguous etiology, the suspected lesion should be confirmed with cytology or histopathology. If biopsy is not possible, the subject should continue therapy, and a follow-up

imaging evaluation (in no less than 4 weeks) should be performed. If repeat scans or cytology/histology confirm recurrence, then recurrence should be declared using the date of the initial scan. For clinically clear recurrence case, the diagnosis can be done by imaging only.

Criteria used to determine CT lymph node metastases were a lymph node diameter at least 1 cm in short axis. The appearance of new malignant lesions denotes disease recurrence. The finding of a new lesion should be unequivocal: ie, not attributable to differences in scanning technique, change in imaging modality or findings thought to represent something other than tumor. A lesion identified on a follow-up study in an anatomical location that was not scanned at baseline is considered a new lesion and will indicate disease recurrence, unless found to be secondary or concurrent malignancy which is non-esophageal or non-gastro-esophageal junction-originated malignancy. An example of this is the subject who has CT or MRI brain scan ordered in the on treatment phase which reveals metastases. The subject's brain metastases are considered to be evidence of recurrence even if he/she did not have brain imaging at baseline.

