4 ENDPOINTS

4.1 Efficacy Endpoints

4.1.1 Disease Free Survival

DFS is the primary endpoint.

Disease-Free Survival is time between randomization date and first date of recurrence or death, whichever occurs first. Recurrence is defined as the appearance of one or more new lesions, which can be local, regional, or distant in location from the primary resected site (by imaging or pathology). DFS will be programmatically determined based on the disease recurrence date provided by the investigator. For subjects who remain alive and without recurrence, DFS will be censored on the date of last evaluable disease assessment. The on-study disease assessment considers CT scan, MRI and biopsy

Detailed censoring rules for the primary definition of DFS are presented in Table 4.1.1-1; graphical display is presented in [Figure 2](#).

Table 4.1.1-1: Censoring Scheme Used in the Primary Definition of DFS

[figure not shown]
Situation	Date of Event or Censoring	Outcome
Recurrence (a) (c) (d) (e)	Date of first recurrence	Event
Death (b) (c) (d) without recurrence	Date of death	Event
No baseline disease assessment	Date of randomization	Censored
No on-study disease assessments and no death (d)	Date of randomization	Censored
Death with prior subsequent therapies or second non-esophageal and non-GEJ primary cancer (d)	Date of randomization	Censored
No recurrence and no death (d) (e)	Date of last evaluable disease assessment	Censored
New anticancer therapy, tumor-directed radiotherapy, or tumor-directed surgery received or the second non-esophageal and non-GEJ primary cancer date without recurrence or death reported prior to or on the same day of disease assessment (d) (e)	Date of last evaluable disease assessment prior to or on the same date of initiation of subsequent therapy or the second non-esophageal and non-GEJ primary cancer date whichever is earlier	Censored

Table 4.1.1-1: Censoring Scheme Used in the Primary Definition of DFS

(a) recurrence = appearance of one or more new lesions, which can be local, regional, or distant in location from the primary resected site
(b) All deaths will be included as DFS event - regardless of cause or of how long it has been since the last known disease evaluation.
(c) Without receiving preceding new anticancer therapy, tumor-directed radiotherapy, tumor-directed surgery, or second non-esophageal and non-GEJ primary cancer.
(d) Without baseline disease.
(e) With on-study disease assessment.

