- *Analysis accounting for assessment on/after subsequent therapy:* DFS will be defined similarly to the primary definition except that events (recurrence or death) and disease assessments that occurred on or after subsequent anti-cancer therapy will be considered (no time point truncation). Although the statistical significance will be determined by the stratified log-rank test using the primary definition of DFS, This analysis will be used to support EMEA filing.
- *DFS accounting for two or more consecutively missing disease assessments prior to DFS event:* This analysis will be performed only if at least 10% of DFS events have two or more consecutively missing prior to disease assessments. In case a subject has two or more consecutively missing disease assessments, the subject will be censored at the last disease assessment date prior the DFS event.
- Analysis in which recurrence-free subjects who are lost to follow-up for any cause will be considered as having an event at the time of the last tumor assessment date prior to loss to follow-up.

Each of the above analysis will use the same significance level as the corresponding primary analysis. Estimate of the HR, its two sided $100(1-\alpha)\%$ CI and p-value will be presented.

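### Do partial start dates for subsequent radiotherapy or surgery remove enough recurrences from primary DFS to need a new imputation rule?

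*SAP*

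**What the plan says.** SAP Section 8 sends missing and partial radiotherapy and surgery dates to Appendix 2. For surgery after the start of treatment with only the day missing, the rule is "If month and year of surgery don't match month and year of first dose date then impute as first day of that month"; in the month of first dose it uses the first dose date. For a year-only date, "If both day and month are missing then impute as maximum between 01JAN of the year and date of the first dose". The radiotherapy rule in the same appendix matches: "If month and year of procedure don't match month and year of first dose date then impute as first day of that month". No visible line compares the imputed start with the recurrence date.

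Footnote (c) of SAP Table 4.1.1-1 limits primary DFS events to those "Without receiving preceding new anticancer therapy, tumor-directed radiotherapy, tumor-directed surgery, or second non-esophageal and non-GEJ primary cancer". When therapy comes first, the subject is censored at the "Date of last evaluable disease assessment prior to or on the same date of initiation of subsequent therapy".

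SAP 7.5.2.1 also plans a DFS analysis that counts recurrences, deaths and assessments after subsequent therapy, with no cut-off at the start of that therapy. Significance is still judged on the primary definition.

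**The concern.** Order decides whether a recurrence is an event or a censoring, and an early imputed date biases that order in one direction. Suppose a scan on 18 May shows recurrence and the radiotherapy given for it is recorded only as May. The imputed start is 1 May, therapy now appears to precede recurrence, and the subject is censored at the last scan on or before 1 May. With 12-weekly imaging that can be almost three months earlier. A true event would be lost because it was treated.

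The neighbouring rules make this look like an oversight. Imputed death dates are checked against the last date known alive, imputed recurrence dates against death, and imputed radiotherapy end dates against death or last known alive. Therapy start dates have no visible check. If many events were lost, or were lost unevenly between arms, the primary hazard ratio would be affected.

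**Working it through.** **Reversal rate per partial date.** Let L be the days from recurrence to the true start of therapy. With only the day missing, the order reverses when both dates fall in the same calendar month and the recurrence is not on the 1st. The share is about (30.4375 − 1 − L)/30.4375; for L = 7, 22.4375/30.4375 = 0.737. For year-only dates it is about (365.25 − 1 − L)/365.25, an upper bound because the first-dose floor is ignored. The day-missing columns below come from exact enumeration over 1,461 calendar days. The last column is the error of the alternative rule (never impute therapy before a recurrence it could have followed) when therapy truly began L days *before* recurrence; it is about (30.4375 − L)/30.4375.

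| L (days) | Plan's rule, day missing | Plan's rule, year only | Alternative rule, day missing |
|---|---|---|---|
| 7 | 74% | 98% | 77% |
| 14 | 51% | 96% | 54% |
| 21 | 28% | 94% | 31% |
| 28 | 5% | 92% | 8% |
| 30 or more | 0% | 88% at 42 | – |

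Protocol 5.4.1 says of equivocal lesions "If repeat scans or cytology/histology confirm recurrence, then recurrence should be declared using the date of the initial scan", and the repeat scan comes at least 4 weeks later. If treatment waits for that confirmation, L is 28 days or more and at most 5% of day-missing dates reverse. Protocol 5.4.2 asks for tissue confirmation to be attempted where feasible, which also tends to lengthen the gap.

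**Number of events lost.** The documents give no count of partial dates, so all three factors are assumptions: lost events = 440 × share first treated with radiotherapy or surgery × share of those lacking the day × share reversed.

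- Low: 440 × 0.10 × 0.01 × 0.05 = 0.02
- Middle: 440 × 0.20 × 0.03 × 0.20 = 0.53
- High: 440 × 0.30 × 0.05 × 0.50 = 3.3

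A much harsher set (350 recurrences, 60% treated locally, 10% partial, 14-day gap) gives 350 × 0.6 × 0.10 × 0.507 = 10.6, or about 20 if every partial date were year-only.

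**Power.** SAP 5.3 states about 91% with 440 events, HR 0.72, two-sided 0.05 and 2:1 allocation. Power = Φ(√(d × 2/9) × |ln 0.72| − 1.96). For d = 440: √97.78 × 0.3285 = 3.248; 3.248 − 1.96 = 1.288; power 90.1%. Adding the interim look at 374 events gives 89.5%. Both are within 2 points of the SAP. In the fixed design, 3, 5, 10 or 20 fewer events give 89.9%, 89.8%, 89.5% or 88.8%.

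These losses are overstated, because both DFS looks are triggered by event counts. From SAP Table 5.1-3, (440 − 374)/(58 − 48) = 6.6 events per month, so replacing one lost event takes 30.4375/6.6 = 4.6 days.

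**Hazard ratio.** In 3,000 simulated trials (760 subjects, 2:1, control hazards from SAP Table 5.1-1 with hazard ratios of 1, 0.667 and 0.8, cut at 440 events), 1, 3 or 5 events drawn at random were censored 12 weeks earlier. The mean ratio of hazard ratios was 1.000 each time. Scaled to 0.72, the central 95% was 0.717–0.724, 0.712–0.732 and 0.707–0.734.

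**All losses in one arm.** Nivolumab's simulated share of events was 0.618, about 272 of 440, against 168 on placebo. Five losses all on nivolumab would multiply the HR by roughly 267/272 = 0.982 (to 0.707), with probability 0.618⁵ = 9%. All five on placebo would multiply it by roughly 168/163 = 1.031 (to 0.742), with probability 0.382⁵ = 0.8%.

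**The case for a change.** The best case for a change is that the rule treats better data worse. If the recurrence also lacks its day, both dates become the 1st, therapy does not precede, and the event stands; only a fully dated recurrence is lost. A later death does not recover it, because footnote (c) covers deaths too. A year-only start in the first-dose year becomes the first dose date, which discards nearly all follow-up. Protocol 3.4.1 prohibits radiotherapy before recurrence (it does not name surgery), so for radiotherapy the imputed order is usually the wrong one. The analysis without truncation does not decide significance. It also restores events that truly followed therapy, so it cannot isolate the effect of imputation.

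All of that is correct on the visible text. What it does not supply is a consequence. Several conditions must coincide: a partial start date, a fully dated recurrence, local rather than systemic therapy first (systemic dates follow another specification), and, for day-missing dates, a start in the same calendar month. The treatment is double-blind, so there is no stated reason for losses to favour an arm. SAP 7.5.2 tabulates by arm the subjects censored for subsequent therapy, and SAP 7.4.3.2 lists that therapy. Only a mark showing that the order was imputed is missing. The text after Appendix 2 is redacted and Section 8 says its conventions may be used, so a check elsewhere cannot be excluded.

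**Conclusion.** No change to the plan. The reversal can happen, but the likely loss is between zero and about three events of 440, with no shift in the mean hazard ratio and about 0.2 points of power at three events. This rests on assumed frequencies of local therapy and partial dates, and on losses unrelated to arm. Even the harsh assumption of 20 lost events costs 1.3 points (90.1% to 88.8%) before allowing for the event trigger. Only many year-only dates concentrated in one arm would alter the conclusion, and nothing in the documents suggests that.

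The existing rule is fixed without reference to outcome and agrees with SAP Section 8, which also sets day-missing recurrence and death dates to the 1st. The alternative depends on whether a recurrence was seen and always resolves doubt towards an event. At equal gaps its error rate is slightly higher (77/54/31/8% against 74/51/28/5%), although for radiotherapy the order it gets wrong should be the rarer one.

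Timing also limits any gain. The rationale for Revised Protocol 04 says "OS event tracking commenced in 2021 after the first planned interim analysis was completed", and SAP 5.4 places the DFS interim analysis at the first interim look. No visible text shows a DFS look still to come, and the primary derivation of a completed look should stay as it was run. Analysts may mark imputed orders in the existing therapy listing; that does not alter what the trial can conclude.
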